#### 8.2.3 Dose escalation.

The maximum tolerated dose (MTD) is defined as the dose with the DLT rate of 30%. Starting at the first dose level of 200mg PO daily, if there are < 1 DLT then it is acceptable to escalate to the next dose level. If no DLT is observed at the first dose level (200mg PO daily) with 3 subjects, then dose escalation will continue with dosing groups of 3 subjects at a time. This will continue up to dose level 2 (400mg of vorinostat). The DLT assessment period is the first 21 days of treatment.

If a DLT is observed at 200 mg PO daily, then the vorinostat dose will be de-escalated to 100 mg PO daily with the intent of increasing the dose back to 200 mg PO daily if 100 mg PO daily is shown to be safe and well-tolerated. After the first DLT is observed or any proposed dose level is achieved without any DLTs, subsequent dose assignments are guided by the modified continuous reassessment method (mCRM) as described below.

The mCRM works in the following way. If n subjects have been assigned and completed 21 days of follow-up, let Yi=1 if the ith subject experienced DLT and let Yi=0 otherwise, for i = 1,..., n. The mCRM model (O'Quigley et al. 1990) used here is

Prob(Yi=1|dose level k)= $\mathbf{F}(\theta, \text{dose level k}) = \exp(3 + \theta \times \text{dose}_{(k)}^*)/(1 + \exp(3 + \theta \times \text{dose}_{(k)}^*)$ 

where  $\theta$  is the parameter to be estimated for the model,  $\mathbf{F}$  is the probability of a subject i experiencing a DLT at dose level k, the dose(k)\* is the standardized dose. The prior distribution on parameter  $\theta$  is assumed to be a gamma distribution with shape=1 and scale=1. The Bayes' theorem is used to update the prior distribution of  $\theta$ . After each subject's response is observed, the mean posterior density of the parameter,  $\theta$ , is computed.

The dose to be administered to the next subject is the dose  $x_{n+1}$  such that  $|Prob(y=1| x_{n+1}, \theta^{(n)}) - 0.3|$  is minimized (i.e., the dose with the estimated DLT rate closest to the target rate of 0.3). When a dose is escalated, skipping dose levels is not allowed so that any escalation would only be to the next higher dose level in the predefined sequence. When a dose is deescalated, a dose level can be skipped.

The total sample size of the dose escalation followed by the mCRM to obtain the estimate of the MTD is 12 subjects. After each dosing group, the mCRM will provide a current estimate of the MTD, which will be recommended as the next dose. The DMC will determine when these estimates of the MTD become consistent to declare the MTD.

Here is one hypothetical example (Table 11 and Figure 5) to illustrate how the mCRM works. Figure 6 summarizes the results of posterior probability of DLT in each dose and suggests the 400mg as the recommended dose (MTD).

- Assign the first 3 patients to the dose 200mg. 0 DLT is observed. The estimated toxicity rate is 1.1% in dose 100mg, 4.6% in dose 200mg, 10.9% in dose 400mg. The dose cohorts, 400mg, have a toxicity rate closer to 30% compared to the one in dose 200mg. Since dose-skipping during escalation is not allowed, the dose 400mg is chosen for the next 3 patients.
- 2. Assign 4-6 patients to the dose 400mg. 1 DLT is observed. The estimated toxicity rate is 2% in dose 100mg, 10.3% in dose 200mg, 25.5% in dose 400mg. Dose cohort, 400mg, has a toxicity rate closest to the target toxicity rate (30%), so the dose 400mg is chosen for the next 3 patients by the mCRM algorithm.
- 3. Assign 7-9 patients to the dose 400mg. 1 DLT is observed. The estimated toxicity rate is 1.9% in dose 100mg, 11.4% in dose 200mg, 28.7% in dose 400mg. Dose cohort, 400mg, has a toxicity rate closest to the target toxicity rate (30%), so the dose 400mg is chosen for the next 3 patients by the mCRM algorithm.
- 4. Assign 10-12 patients to the dose 400mg. 1 DLT is observed. The estimated toxicity rate is 1.8% in dose 100mg, 11.7% in dose 200mg, 30.1% in dose 400mg. Dose cohort 400mg has a toxicity rate closest to the target toxicity rate (30%). And it reaches the maximum of the sample size (n=12). The mCRM algorithm claims the dose 400mg as MTD.

Table 11. Hypothetical example of the modified continuous reassessment method (mCRM).

Patient ID	Dose	DLT (DLT=1)		Level -1 (100mg)	Level 1 (200mg)	Level 2 (400mg)
1	200mg	0				
2	200mg	0				
3	200mg	0				
			Estimated toxicity rate at end of this	1.10%	4.60%	10.90%

			dose 200mg			
				Dose 400m closest to t (30%), so chosen for t	he target t the dose	oxicity rate 400mg is
4	400mg	0				
5	400mg	0				
6	400mg	1				
			Estimated toxicity rate at end of this dose 400mg	2%	10.30%	25.50%
				Dose 400m closest to t (30%), so chosen for t	he target the the	oxicity rate 400mg is
7	400mg	0				
8	400mg	1				
9	400mg	0				
			Estimated toxicity rate at end of this dose 400mg	1.90%	11.40%	28.70%
				Dose 400m closest to t (30%), so chosen for t	he target t the dose	oxicity rate 400mg is
10	400mg	0				
11	400mg	0				
12	400mg	1				
			Estimated toxicity rate at end of this dose 400mg	1.80%	11.70%	30.10%
				The mCRM dose 400mg		claims the

[figure not shown]

Figure 5. Hypothetical example of the modified continuous reassessment method (mCRM).

[figure not shown]

Figure 6. A summary of the results of posterior probability of DLT at each dose level. The model suggests the 400mg as the recommended dose (MTD) depicted by the diamond.

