## 8.2 Statistical Analysis Plan

#### 8.2.1 Phase I dose escalation.

The primary objective of this phase I dose escalation is to find a maximum tolerated dose (MTD) corresponding to a risk of DLT occurring in 30% of patients. Two dose levels have been identified for experimentation (200mg PO daily and 400mg PO daily) with a back-up dose at 100mg PO daily, and due to safety concerns the first cohort of patients will receive the lowest dose (200mg). The study uses the modified continuous reassessment method (mCRM) described later to design dose escalation (O'Quigley et al., 1990). The design will recruit patients in cohorts of three patients each and will not allow for dose-skipping during escalation. A total of 12 patients will be enrolled for the Phase I dose escalation. The initial guess of the risk of DLT at the lowest dose (200mg) is 10% whilst the best guess of the MTD is at dose level 2 (400mg) (i.e., a 30% risk of DLT at this dose level). The initial guesses of risk of DLT are established for each dose level as shown in Table 10.

Table 10. Initial estimates of the probability of DLT at each dose level.

	Dose cohort		
	100mg PO Daily	200mg PO Daily	
	(back-up dose)	(starting dose)	400mg PO Daily
initial guessed DLT probability	1%	10%	30%

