## 8.2.4 Operating characteristics.

**Table 12** shows a simulation study conducted to illustrate the performance of the design in various conditions. Specifically, we explored different scenarios from toxicity as expected and greater than expected. Our initial guess of DLT probability is 1% for 100mg dose, 10%

for 200mg dose, and 30% for 400mg dose). Scenario 1 is the case that our initial guessed of DLT probability is same as the true DLT probability. Scenario 2 and 3 are the case that the true DLT probability is greater than our initial guessed of DLT probability with 100mg and 200 mg as MTD, respectively. Scenario 4 is the same as Scenario 1 except a higher DLT probability in the back-up dose.

Table 12. A simulation study to depict the mCRM design for various conditions. The MTD is highlighted in each scenario.

	100mg	200mg	
	(back-up dose)	(starting dose)	400mg
Prior guess of DLT probability	1%	10%	30%
Scenario 1			
(Toxicity as expected)	1%	10%	30%
Scenario 2			
(greater than expected:			
100mg as MTD)	30%	40%	60%
Scenario 3			
(greater than expected:			
200mg as MTD)	10%	30%	50%
Scenario 4			
(greater than expected:			
400mg as MTD)	5%	10%	30%

Simulation results show that in each of these scenarios, the mCRM study design with 12 subjects is superior to the 3+3 design in estimating the MTD correctly. Table 13 reports the probability of a dose to be selected as MTD (Percent Recommendation) and the probability of patients assigned to each dose level (Percent Experimentation). Ideally, if the mCRM design works well, we expect it will choose the true MTD dose with the highest probability (i.e., highest Percent Recommendation) and assign more patients in the true MTD dose (i.e., highest Percent Experimentation).

In Scenario 1 with 400mg as true MTD, the mCRM design yields a high probability of 83.3% to claim 400mg as MTD. In contrast, the 3+3 design results in 44.8% to claim 400mg as

MTD and 44.8% for 200mg as MTD. Regarding probability of patients assigned to each dose level, ideally we would like to see more patients assigned in the MTD dose. There are 56.7% patients assigned to the 400mg by the mCRM design compared to 42.7% by the 3+3 design.

In Scenario 2 with 100mg as true MTD, the probability to claim 100mg as MTD is 54.5% by the mCRM design and 20.4% by the 3+3 design. There are 34.3% patients assigned to the 100mg by the mCRM design compared to 40.3% by the 3+3 design.

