In Scenario 3 with 200mg as true MTD, the probability of 200mg as MTD is 53.2% by mCRM design and 34.8% by 3+3 design. There are 58.2% patients assigned to the 200mg by the mCRM design compared to 49.4% by the 3+3 design.

In Scenario 4 with 400mg as true MTD, the probability of 400mg as MTD is 83.5% by the mCRM design and 44.8% by the 3+3 design. Both designs have 42.7%-57.3% patients assigned to the 400mg dose level (mCRM: 57.3%; 3+3 design: 42.7%).

These simulations show that the proposed mCRM design with 12 subjects is superior to the 3+3 design in that it has a higher probability of estimating the MTD correctly.

Table 13. The mCRM would allow more patients to be exposed to the MTD as compared to the 3+3 design. The simulation scenarios are associated with a probability of a dose to be selected as the MTD (Percent Recommendation) and a proportion of patients assigned to each dose level (Percent Experimentation).

		Probability of a dose to be selected as MTD  (Percent Recommendation)  Dose Cohort					Probability of patients assigned to each dose level  (Percent Experimentation)			
							Dose Cohort			
	Method	<100mg	100mg	200mg	400mg		100mg	200mg	400mg	
Scenario 1										
(Toxicity as expected:	CRM			16.3	83.3					
400mg as true MTD)	(n=12)	0.0%	0.4%	%	%		1.6%	41.7%	56.7%	
	3+3		10.1	44.8	44.8					
	(n=9.38)	0.3%	%	%	%		5.5%	51.8%	42.7%	
Scenario 2										
(greater than expected:	CRM		54.5	36.6						
100mg as true MTD)	(n=12)	0.0%	%	%	8.9%		34.3%	53.4%	12.3%	

	3+3 (n=10.16)	55.7 %	20.4 %	21.4 %	2.5%	40.3%	48.5%	11.2%
Scenario 3								
(greater than expected: 200mg as true MTD)	CRM (n=12)	0.0%	21.7 %	53.2 %	25.1 %	18.6%	58.2%	23.3%
	3+3 (n=10.57)	16.5 %	40.2 %	34.8 %	8.5%	30.9%	49.4%	19.7%
Scenario 4								
(greater than expected: 400mg as true MTD)	CRM (n=12)	0.0%	1.0%	15.5 %	83.5 %	1.8%	40.9%	57.3%
	3+3 (n=9.38)	1.5%	8.9%	44.8 %	44.8 %	5.5%	51.8%	42.7%

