#### 10.13 Protocol Modifications

No modifications will be made to the protocol without the agreement of the investigators. Changes that significantly affect the safety of the patients, the scope of the investigation, or the scientific quality of the study will require Scientific Review Committee and Institutional Review Board approval prior to implementation, except where the modification is necessary to eliminate apparent immediate hazard to human subjects. Any departures from the protocol must be fully documented in the case report form and the source documentation.

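### Section 8.2.3 gives two rules for a DLT at 200 mg without saying which prevails, and Table 13 simulates the proposed design without the written de-escalation step

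*Combined protocol and SAP*

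**What the plan says.** Phase I treats 12 patients in cohorts of three, starting at 200 mg, with 100 mg as a back-up dose and 400 mg as the top dose (Section 8.2.1). Section 8.2.3 then addresses a DLT at 200 mg in two ways.

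- De-escalation: "If a DLT is observed at 200 mg PO daily, then the vorinostat dose will be de-escalated to 100 mg PO daily", followed by "with the intent of increasing the dose back to 200 mg PO daily if 100 mg PO daily is shown to be safe" and well tolerated.
- Hand-over: once a first DLT has been seen, or a dose level has been reached without one, "subsequent dose assignments are guided by the modified continuous reassessment method (mCRM) as described below". Later in the section, after each dosing group, "the mCRM will provide a current estimate of the MTD, which will be recommended as the next dose".

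No sentence ranks the two rules, sizes the 100 mg cohort, or gives the DLT count at 100 mg that permits a return to 200 mg. The worked example (Table 11) has no DLT in the first cohort, so it never reaches this branch.

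Section 8.2.4 reports the simulated performance of the mCRM against a 3+3 design (Table 13). For Scenario 1 it says "the mCRM design yields a high probability of 83.3% to claim 400mg as MTD", and for Scenario 4 "the probability of 400mg as MTD is 83.5% by the mCRM design". It does not mention the de-escalation step.

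**The concern.** The dose given after a toxicity is the central safety decision of a dose-escalation study. If one of the first three patients has a DLT, one sentence sends the next cohort to 100 mg and another leaves the choice to a model that may pick 200 mg. The team should not have to settle this during the trial.

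The second issue is what Table 13 describes. If the written step governs, the quoted selection probabilities and patient allocations belong to a different design from the one that will be run. The MTD found here is the dose carried into phase Ib and the randomized phase II.

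**Working it through.** **Inputs.** From Sections 8.2.1 to 8.2.4: four cohorts of three, starting at 200 mg; target DLT rate 30%; logit(p) = 3 + θ × dose*; θ ~ gamma(1,1); next dose is the one with estimated DLT rate closest to 0.30; no skipping upward. True DLT rates at 100/200/400 mg (Table 12):

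- Scenario 1: 1/10/30%
- Scenario 2: 30/40/60%
- Scenario 3: 10/30/50%
- Scenario 4: 5/10/30%

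**Assumption.** The standardized doses are not given. I set dose* = (logit(prior guess) − 3)/ln 2, which places the 1/10/30% guesses at the prior median of θ, and used posterior-mean DLT probabilities.

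**Step 1: reproduce the plan.** For the four stages of Table 11 this gives 1.1/4.4/10.7, 1.9/10.3/25.5, 1.9/11.3/28.7 and 1.8/11.7/30.1%. The stated values are 1.1/4.6/10.9, 2/10.3/25.5, 1.9/11.4/28.7 and 1.8/11.7/30.1%. Exact enumeration of the mCRM alone, Scenarios 1-4:

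| | Computed | Table 13 |
|---|---|---|
| Correct selection (%) | 83.3/55.0/53.2/83.3 | 83.3/54.5/53.2/83.5 |
| Share at 100 mg (%) | 1.7/34.3/18.3/1.9 | 1.6/34.3/18.6/1.8 |

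**Step 2: where the rules part.** After 1/3 DLTs at 200 mg the model estimates 17.9/37.5/55.4% at 100/200/400 mg. The distances from 30% are 12.1, 7.5 and 25.4 points, so the mCRM repeats 200 mg. The de-escalation sentence requires 100 mg. After 2/3 or 3/3 DLTs both rules give 100 mg. The probability of exactly 1/3 is:

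- Scenarios 1 and 4: 3 × 0.1 × 0.9² = 24.3%
- Scenario 2: 3 × 0.4 × 0.6² = 43.2%
- Scenario 3: 3 × 0.3 × 0.7² = 44.1%

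**Step 3: the return clause.** After 2/3 DLTs at 200 mg and then 0/3 at 100 mg the model gives 19.0/43.4/62.3%; after 3/3 and then 0/3 it gives 32.4/57.1/72.1%. In both cases it stays at 100 mg, while the clause, if 0/3 counts as safe, points to 200 mg. Under the step, the probability of reaching this point is P(2 or 3 of 3 at 200 mg) × P(0 of 3 at 100 mg):

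- Scenario 1: 0.028 × 0.99³ = 2.7%
- Scenario 2: 0.352 × 0.7³ = 12.1%
- Scenario 3: 0.216 × 0.9³ = 15.7%
- Scenario 4: 0.028 × 0.95³ = 2.4%

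After 1/3 at 200 mg and then 0/3 at 100 mg (8.0/26.0/46.0%) clause and model agree on 200 mg.

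**Step 4: a check that needs no dose-toxicity model.** At a true 10% rate, P(at least one DLT in three) = 1 − 0.9³ = 27.1%. A three-patient 100 mg cohort within the 12 then puts at least 0.271 × 3/12 = 6.8% of patients at 100 mg. Table 13 shows 1.6% (Scenario 1) and 1.8% (Scenario 4), so the step was not simulated. The same bound is uninformative in Scenarios 2 and 3 (19.6% and 16.4%, below the stated 34.3% and 18.6%).

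**Step 5: performance with the step.** A three-patient 100 mg cohort is inserted and counts within the 12; the mCRM makes the final selection. Scenarios 1-4:

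| Design | Correct selection (%) | Share at 100 mg (%) |
|---|---|---|
| Table 13, mCRM as stated | 83.3/54.5/53.2/83.5 | 1.6/34.3/18.6/1.8 |
| Step after first cohort, mCRM decides return | 79.2/63.4/55.1/77.6 | 7.8/49.7/29.3/8.7 |
| Step after first cohort, 0/3 at 100 mg returns | 79.2/60.8/56.1/77.6 | 7.1/45.8/25.0/8.0 |
| Step after first cohort, 0/3 or 1/3 returns | 79.2/57.4/58.1/77.6 | 6.9/37.8/22.0/7.2 |
| Step after every 200 mg cohort with a DLT, mCRM decides return | 76.7/67.7/56.5/75.1 | 10.4/54.6/36.8/11.2 |
| Table 13, 3+3 as stated | 44.8/20.4/34.8/44.8 | 5.5/40.3/30.9/5.5 |

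Against the computed mCRM without the step, the loss in Scenario 1 is 83.3 − 79.2 = 4.1 or 83.3 − 76.7 = 6.6 points; in Scenario 4 it is 83.3 − 77.6 = 5.7 or 83.3 − 75.1 = 8.2 points.

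**The case against.** The strongest reply is that the text already leans one way. The de-escalation sentence is specific and mandatory and comes first; the mCRM only guides later assignments, and its estimate is only recommended. Read in the ordinary way, the next cohort goes to 100 mg and the model takes over afterwards. This has force: a reader might infer that Section 8.2.3 is silent, or that it leaves the two doses equally open, and neither is right. But the better this reply is, the less Table 13 describes the trial, because the simulation leaves that step out.

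A reader might also infer that Table 13 is miscalculated. It is not; its mCRM rows reproduce closely for the mCRM alone. Nor do the results overturn the comparison with 3+3, since every version of the step computed above keeps correct selection above the stated 3+3 rates.

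Finally, it is tempting to read the step as confined to the first cohort. The hand-over sentence supports that, but the de-escalation sentence has no such limit, so both scopes are shown.

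It is also fair to say that the step is the more cautious rule and that correct selection rises in Scenarios 2 and 3. This limits the consequence but does not settle which dose follows 1/3 DLTs.

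**Conclusion.** The point holds as a conflict between two written rules and a simulation that follows only one of them. It should be corrected, but it does not undermine the choice of design or the sample size of 12.

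Two results do not depend on how the doses were standardized: the frequency of 1/3 DLTs (24 to 44% of trials), and the 6.8% minimum share at 100 mg in Scenarios 1 and 4, which assumes only a three-patient cohort within the 12. That the mCRM repeats 200 mg after 1/3 was also found under each of four variants tried (two dose scalings, two estimators). The selection probabilities with the step depend on the inferred standardized doses, which reproduce Table 11 within 0.2 points, and on the scope and return rule assumed. Across the versions shown, correct selection falls by about 4 to 8 points in Scenarios 1 and 4 and rises in Scenarios 2 and 3.

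**What to change.** State in Section 8.2.3:

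- that de-escalation to 100 mg overrides the mCRM after a DLT at 200 mg;
- whether this applies to the first cohort only or to every 200 mg cohort with a DLT;
- the size of the 100 mg cohort;
- the DLT count at 100 mg that allows return to 200 mg, or that the mCRM decides.

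Then re-run the simulation and restate Table 13 and the 83.3% and 83.5% in Section 8.2.4. The cost is a few sentences and a re-run, plus lower quoted figures in the two scenarios where 400 mg is the MTD.

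If the mCRM is meant to govern at once, remove the de-escalation sentence; Table 13 then stands and no re-run is needed. That takes out a written dose-reduction safeguard in a part whose starting dose was chosen on safety grounds, so it should be a deliberate decision under Section 10.13, where a modification with a significant effect on patient safety needs sign-off from the scientific review body and the IRB before it takes effect.

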#### **5.2 Trial Treatments**

The phase I dose escalation will include a fixed dose of Pembrolizumab 200mg IV every 3 weeks and escalating doses of vorinostat (three dose levels) to determine the MTD to be used in the expansion group and the randomized phase II portion of the trial. Once a MTD is determined, the phase Ib expansion and randomized phase two portions of the trial can begin accrual. Cycle 1, day 1 will start with Pembrolizumab concurrent with continuous daily oral therapy with vorinostat.

Table 6. Vorinostat dose levels in phase I dose escalation phase.

Dose Level	Vorinostat Dose, Route, Frequency	Pembrolizumab Dose, Route, Frequency	Use
-1	100mg PO Daily	200mg IV Q3 weeks	Experimental
1	200mg PO Daily	200mg IV Q3 weeks	Experimental
2	400mg PO Daily	200mg IV Q3 weeks	Experimental

Trial treatment should begin within 3 days of randomization or as close as possible to the date on which treatment is allocated/assigned.

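### Section 8.2.3 gives two different next doses after one DLT in three patients at 200 mg, and Table 13 matches only the rule that ignores the 100 mg sentence

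*Combined protocol and SAP*

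**What the plan says.** Section 8.2.3 starts at 200 mg in cohorts of three and gives two instructions for what follows a DLT there.

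- The dose step: "If a DLT is observed at 200 mg PO daily, then the vorinostat dose will be de-escalated to 100 mg PO daily", with a planned return to 200 mg if 100 mg is tolerated.
- The model: "After the first DLT is observed or any proposed dose level is achieved without any DLTs, subsequent dose assignments are guided by the" mCRM, which picks "the dose with the estimated DLT rate closest to the target rate of 0.3". The section adds that the mCRM estimate after each dosing group is the recommended next dose.

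Nothing says which prevails. The worked example in Table 11 has no DLT at 200 mg, so it does not settle the matter.

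Section 8.2.4 and Table 13 then report how the design performs. For example: "In Scenario 1 with 400mg as true MTD, the mCRM design yields a high probability of 83.3% to claim 400mg as MTD", and for Scenario 2, "There are 34.3% patients assigned to the 100mg by the mCRM design compared to 40.3% by the 3+3 design".

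**The concern.** With two or three DLTs in the first cohort, both instructions lead to 100 mg. With exactly one they may not, and this is a common outcome. If they differ, the text does not settle whether the next three patients receive 100 mg or stay at 200 mg, and the reported operating characteristics can be right for only one answer.

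The result carries forward. Section 5.2 says "Once a MTD is determined, the phase Ib expansion and randomized phase two portions of the trial can begin accrual", so the declared MTD sets the vorinostat dose for 18 phase Ib patients and up to 39 patients in Arm B.

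**Working it through.** **Inputs.** From 8.2.1, 8.2.3 and 8.2.4: four cohorts of 3 (n = 12), start at 200 mg, no skipping upward, target 30%; logit p = 3 + θ·d with θ ~ Gamma(1,1); prior guesses 1/10/30% at 100/200/400 mg. True rates at 100/200/400 mg in Scenarios 1 to 4 (S1 to S4) are 1/10/30, 30/40/60, 10/30/50 and 5/10/30%.

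**Step 1: recover the fitted model.** The text does not say how d is scaled. Six variants were tried: scaling at the prior mean or prior median of θ, crossed with plug-in posterior mean of θ, plug-in posterior median, or posterior mean of p. All paths were enumerated exactly. Prior-median scaling (θ = 0.693) with the posterior mean of p fits best. For instance d(200 mg) = (logit 0.10 − 3)/0.693 = (−2.197 − 3)/0.693 = −7.50.

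It nearly reproduces Table 11 (100/200/400 mg, %):

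| After cohort | Printed | Computed |
|---|---|---|
| 1 | 1.1/4.6/10.9 | 1.1/4.4/10.7 |
| 2 | 2/10.3/25.5 | 1.9/10.3/25.5 |
| 3 | 1.9/11.4/28.7 | 1.9/11.3/28.7 |
| 4 | 1.8/11.7/30.1 | 1.8/11.7/30.1 |

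**Step 2: next dose after the first cohort at 200 mg.**

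- 1/3 DLTs: estimates 17.9/37.5/55.4%. Distances from 30% are 12.1, 7.5 and 25.4 points, so the mCRM stays at 200 mg while the sentence says 100 mg. All six variants stay at 200 mg.
- 2/3 DLTs: estimates 48.9/66.9/77.6%, so both rules give 100 mg. They also agree at 3/3.

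P(exactly 1/3) = 3p(1−p)²: 3 × 0.1 × 0.81 = 24.3% (S1, S4); 3 × 0.4 × 0.36 = 43.2% (S2); 3 × 0.3 × 0.49 = 44.1% (S3).

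**Step 3: which rule did Table 13 simulate?** A check that needs no model: in S1 and S4 the chance of at least one DLT in the first cohort is 1 − 0.9³ = 27.1%. If those trials send the next three of 12 patients to 100 mg, the share treated there is at least 0.271 × 3/12 = 6.8%. Table 13 prints 1.6% and 1.8%.

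The model-based check, using the best-fitting variant:

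| | S1 | S2 | S3 | S4 |
|---|---|---|---|---|
| **Share of patients at 100 mg, %** | | | | |
| Printed, Table 13 | 1.6 | 34.3 | 18.6 | 1.8 |
| mCRM only | 1.7 | 34.3 | 18.3 | 1.9 |
| 100 mg if the trial's first DLT is at 200 mg, then mCRM | 7.8 | 49.7 | 29.3 | 8.7 |
| 100 mg after any DLT at 200 mg | 10.4 | 54.6 | 36.8 | 11.2 |
| **Correct selection, %** | | | | |
| Printed, Table 13 | 83.3 | 54.5 | 53.2 | 83.5 |
| mCRM only | 83.3 | 55.0 | 53.2 | 83.3 |
| 100 mg if the trial's first DLT is at 200 mg, then mCRM | 79.2 | 63.4 | 55.1 | 77.6 |
| 100 mg after any DLT at 200 mg | 76.7 | 67.7 | 56.5 | 75.1 |

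The mCRM-only rule matches every mCRM entry of Table 13 within 0.5 points. Across the six variants, the S1 share at 100 mg is 1.0–1.7% under mCRM only, 7.1–7.8% under the first 100 mg reading and 9.0–10.4% under the second. The number of phase I simulation runs is not stated. Assuming only 100, the standard error of the 7.8% is 1.4 points, so the gap to 1.6% is not simulation noise.

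**Step 4: a side effect of mCRM-only dosing.** Four cohorts at 200 mg with 1, 1, 0, 0 DLTs end at 17.8% for 200 mg and 38.8% for 400 mg. The distances are 12.2 and 8.8 points, so the model names 400 mg with nobody treated there. The path's probability is [3p(1−p)²]² × [(1−p)³]². In S1 that is 0.243² × 0.729² = 3.1%; S2 to S4 give 0.9, 2.3 and 3.1%. It occurs under all six variants, and never under either 100 mg reading.

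**The case against.** The strongest reply is that 8.2.3 can be read in sequence: a rule-based first step (100 mg after a DLT at 200 mg), with the mCRM taking over for assignments after that. The specific instruction then comes before the general one and there is no conflict. This reading is possible, but it moves the fault to Table 13, which does not describe that trial.

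Three further points have weight. The model-free floor is decisive only in Scenarios 1 and 4; in Scenarios 2 and 3 the floors are 19.6% and 16.4%, below the printed 34.3% and 18.6%, so the mismatch there rests on the reconstructed model. The best-fitting estimator is also not the plug-in posterior mean that 8.2.3 describes. That plug-in does not reproduce Table 13 even under mCRM-only dosing: 58.8–60.4% correct in Scenario 3 against 53.2% printed. So the restated selection figures carry a range. Over the six variants, the sequential reading gives 76.3–80.7%, 56.8–63.6% and 55.1–62.0% in Scenarios 1 to 3, with a Scenario 1 loss of 1.7–4.2 points. The direction is the same in every variant. Finally, the 100 mg sentence is the cautious rule, so following it does not expose patients to a higher dose.

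The DMC's role does not close the gap. "The DMC will determine when these estimates of the MTD become consistent to declare the MTD" concerns declaring the MTD, not choosing between two next-dose rules.

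**Conclusion.** The concern holds. After 1/3 DLTs at 200 mg, the text supports both 100 mg and 200 mg, in a situation with probability 24.3% to 44.1%. Table 13 and the 83.3% in 8.2.4 belong to mCRM-only dosing. Following the sentence lowers correct selection by about 4 to 8 points in Scenarios 1 and 4 and raises it by about 2 to 13 points in Scenarios 2 and 3, using the best-fitting variant.

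The existence of the conflict does not depend on which of the six estimators is used, and the Table 13 mismatch in Scenarios 1 and 4 needs no model. The exact selection figures rest on the inferred dose scaling and estimator. The claim that the mCRM beats 3+3 is not at risk: the lowest correct-selection figures in the table above are 76.7, 55.0, 53.2 and 75.1%, against 44.8, 20.4, 34.8 and 44.8% printed for 3+3.

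**What to change.** State in 8.2.3 which rule sets the next dose after a DLT at 200 mg. The choice is the sponsor's.

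- **A. The 100 mg sentence governs.** Say whether it applies only when the trial's first DLT is at 200 mg or after any DLT at 200 mg. Rerun Table 13 and the figures in 8.2.4. Scenario 1 correct selection is then restated from 83.3% to about 79.2% or 76.7%.
- **B. The mCRM governs.** Delete the 100 mg sentence. Add that the declared MTD may not exceed the highest level given to DLT-evaluable patients (an upward limit only), and update Table 13. Correct selection falls from 83.3% to 80.2% in Scenarios 1 and 4, stays at 55.0% in Scenario 2, and rises from 53.2% to 55.5% in Scenario 3.

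Both options cost some wording and one simulation rerun, with no extra patients. The rerun should also state the dose scaling and the estimator used.

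Optional, and separate from the conflict: say that the DMC may reject a level on its observed DLTs. With 0/9 at 200 mg and 3/3 at 400 mg, the model names 400 mg at patient 12 (16.9% against 37.6%), in 1.05, 0.22 and 0.50% of trials in Scenarios 1 to 3. No numeric cutoff is proposed.

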## 5.9 Subject Replacement Strategy

#### 5.10 Clinical Criteria for Early Trial Termination

Early trial termination will be the result of the criteria specified below:

- 1. Quality or quantity of data recording is inaccurate or incomplete
- 2. Poor adherence to protocol and regulatory requirements
- 3. Incidence or severity of adverse drug reaction in this or other studies indicates a potential health hazard to subjects
- 4. Plans to modify or discontinue the development of the study drug

In the event of Merck decision to no longer supply study drug, ample notification will be provided so that appropriate adjustments to subject treatment can be made.

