# 10.8 The Protocol Monitoring Committee (PMC)

The PMC meets once a month. The PMC reviews and evaluates safety and/or efficacy data for all physician authored clinical intervention trials. The PMC ensures the safety of patients and the validity and integrity of data. PMC reviews SAEs, deviations, Interim analysis, interim and final reports from the external Data Monitoring Committee (DMC) as well as audits both internally and externally. The PMC can make the following determinations, Accepted, Acceptable with Corrective Action and Tabled.

Investigators of studies, which are designated to be reviewed by the PMC for data and safety monitoring, shall provide an interim analysis report of the study's progress and summary of adverse events and deviations based on the phase of the study and the associated risk of the study or more often if applicable. The external DSMB (if applicable) shall forward its report for high-risk studies designated for external review at least annually or more often if applicable.

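### The dose-finding rule in 8.2.3 always names a dose, and no written DLT limit stops it at 100 mg: a cheap safeguard against an unlikely case

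*Combined protocol and SAP*

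**What the plan says.** Section 8.2.1 gives two planned vorinostat doses, 200 and 400 mg daily, with 100 mg as a back-up. Cohorts are of three, 12 patients in all. Section 8.2.3 defines the MTD as the dose with a DLT rate of 30%, and each next dose is "the dose with the estimated DLT rate closest to the target rate of 0.3".

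After a DLT at 200 mg, 8.2.3 drops the dose to 100 mg, intending to go back up "if 100 mg PO daily is shown to be safe and well-tolerated". It does not say what follows if 100 mg is not tolerated.

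The model output is a recommendation. The declaration belongs to a committee: "The DMC will determine when these estimates of the MTD become consistent to declare the MTD". Section 5.2 gives the consequence: "Once a MTD is determined, the phase Ib expansion and randomized phase two portions of the trial can begin accrual".

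Table 12 has four scenarios, and the highest true rate at 100 mg is 30% (Scenario 2). Table 13 has a column for a result below 100 mg. The CRM shows 0.0% there in every scenario; the 3+3 comparator shows 55.7% in Scenario 2.

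**The concern.** A minimum distance over three doses always has a winner. If all three estimates lie far above 30%, the rule names the smallest of them, which is 100 mg. Consistency is no protection, because an algorithm that stays at 100 mg with a high estimate is entirely consistent.

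A declared MTD opens phase Ib (18 patients) and Arm B of the randomised part (23 in stage 1, up to 39), so up to 18 + 39 = 57 patients could receive the declared dose. If the combination were too toxic at 100 mg, the only protection would be judgement, with no limit fixed beforehand and none simulated. The statement in 8.2.4 that "Simulation results show that in each of these scenarios, the mCRM study design with 12 subjects is superior to the 3+3 design" rests on scenarios that do not include this case.

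**Working it through.** **Inputs.** From 8.2.1, 8.2.3 and Table 10: logit p(k) = 3 + θ·d(k); θ ~ Gamma(1,1); initial guesses 1/10/30%; target 30%; four cohorts of three; start at 200 mg; no skipping on the way up. The standardised doses d(k) are not given.

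**Assumption on d(k).** Take d(k) = (logit(guess) − 3)/c and choose c to fit Table 11. With c = 0.710:

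- 100 mg: (−4.595 − 3)/0.710 = −10.70
- 200 mg: (−2.197 − 3)/0.710 = −7.32
- 400 mg: (−0.847 − 3)/0.710 = −5.42

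**Reproducing the plan's figures.** Using posterior-mean probabilities, all 12 estimates in Table 11 come back within 0.05 point. Exact enumeration of every cohort outcome gives correct selection of 83.3/55.0/53.2/83.3% in Scenarios 1 to 4, against 83.3/54.5/53.2/83.5% in Table 13, and 0.0% below 100 mg throughout.

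**The rule at an extreme.** After 3/3 DLTs at 200 mg and 3/3 at 100 mg the estimates are 86.1/90.2/92.0%. The distances from 0.30 are 0.561, 0.602 and 0.620, so 100 mg is still named. This path is rare:

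- Scenario 2: 0.4³ × 0.3³ = 0.2%
- 40/50/70%: 0.5³ × 0.4³ = 0.8%
- 50/60/70%: 0.6³ × 0.5³ = 2.7%

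**The ordinary case, and the proposed rule.** The toxic rates are assumed; the documents give none. The rule stops with no MTD once 100 mg has been tried and Pr(p at 100 mg > 0.30) > 0.95.

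| True rates 100/200/400 mg | 40/50/70% | 50/60/70% |
|---|---|---|
| Current: returns no dose | 0% | 0% |
| Current: names 100 mg | 78.4% | 92.0% |
| Current: names 100 mg with its own estimate above 30% | 58% | 81% |
| With rule: stops | 14.9% | 34.8% |
| With rule: still names 100 mg | 63.5% | 57.2% |

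**Price of the rule where some dose is tolerable.** False stops are 0.0/4.4/0.1/0.0% in Scenarios 1 to 4. Correct selection falls from 55.0% to 50.6% in Scenario 2 and is unchanged in Scenarios 1, 3 and 4.

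**When it acts after one cohort at each dose (200 mg, then 100 mg).**

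| DLTs | Pr(p at 100 mg > 0.30) | Action |
|---|---|---|
| 3/3, 2/3 | 0.98 | stop |
| 2/3, 3/3 | 0.99 | stop |
| 2/3, 2/3 | 0.91 | continue |
| 3/3, none treated at 100 mg | 0.94 | continue |

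**Sensitivity.** The variants are posterior-mean or plug-in estimates, with or without the forced drop to 100 mg after a first-cohort DLT. Across them, 100 mg is named in 73–84% and 90–95% of trials; the 0.95 rule stops 14.9–18.6% and 34.7–39.9%; and false stops in Scenario 2 are 4.4–6.1%. With c = 0.693 (the prior median), selection and stopping figures are the same. With c = 1.0 the fit to Table 11 is off by up to 3.9 points, and stops become 20.2% and 43.3%, with 6.4% false stops in Scenario 2.

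**The case against.** The strongest reply is that the algorithm does not act alone. The MTD is a defined term, so a DMC looking at an 86% estimate could not properly declare 100 mg to be one. Section 5.10 lists among its termination criteria that "Incidence or severity of adverse drug reaction in this or other studies indicates a potential health hazard to subjects", and is worded as mandatory. Section 10.8 adds that "The PMC reviews and evaluates safety and/or efficacy data for all physician authored clinical intervention trials". Sections 10.9 and 10.10 let the PMC, IRB, investigator or sponsor halt the study. This stands. A reader might infer that nothing could stop dosing at 100 mg, or that the DMC has no standard but consistency; the documents do not support either. What remains is narrower: none of these provisions gives a DLT count or rate for 100 mg, and none is in the simulation.

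The triggering case is also unlikely. Section 4.2.1 reports a single-agent vorinostat MTD of 400 mg daily, four times the back-up dose; no DLTs at 200 mg twice daily in another trial; 6% grade 3/4 drug-related events with pembrolizumab alone; and little overlap of toxicities. This stands too, and sets the priority of the point.

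A reader might take 78% and 92% as the size of the gap. They include trials where the estimate at 100 mg is at or below 30%, which is sampling error with 12 patients. A reader might also conclude from the 55.7% in Table 13 that 3+3 is the better design. In Scenario 2, 100 mg is the true MTD, so those are wrong stops; the figure shows only that 3+3 can return no dose.

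Finally, the remedy is modest. At 40/50/70%, 43.1% of trials would still name 100 mg with an estimate above 30%, and the documents give no basis for 0.95 over another cut-off. Both points are fair.

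**Conclusion.** The point holds as a low-cost safeguard against a low-probability event. As written, the algorithm cannot return a finding of no MTD, and no provision sets a DLT limit at 100 mg. The direct size of the gap is 58% and 81% of trials under assumed true rates of 40/50/70% and 50/60/70%, where the algorithm names 100 mg against its own estimate.

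These are outputs of the algorithm. A discretionary halt would lower them by an amount the documents do not allow to be computed. They also rest on the dose standardisation inferred from Table 11, which matters for precision and not for the logical gap. A reader might infer that the planned doses are unsafe; the prior data in 4.2.1 point the other way.

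**What to change.** Add to 8.2.3: *Once at least one cohort has been treated at 100 mg, if the posterior probability that the 100 mg DLT rate exceeds 30% is above 0.95, dose finding stops and no MTD is declared.* Make the DMC's declaration subject to this rule. Re-run Table 13 with it, add one scenario with 100 mg above 30% (for example 40/50/70%), and state the dose standardisation.

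The cost is a paragraph and a simulation re-run, with no added patients, plus the 4.4-point loss of correct selection in Scenario 2.

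The cut-off is for the sponsor to calibrate. At 0.90 the rule stops more of the toxic cases (29.2% and 53.8%), but false stops rise to 11.5% in Scenario 2 and 0.7% in Scenario 3, and correct selection in Scenario 2 drops to 43.5%. Requiring that 100 mg has been tried matters more at that cut-off: without it, false stops would be 15.5% and 3.3%.
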